5.5 Rationale for Injection of Second Submandibular Gland

We have achieved our primary objective of evaluating the safety and tolerability of injection of interferon gamma stimulated MSCs into the submandibular gland. No patients have had a DLT within one month of injection. Indeed, only 3 patients reported pain (pain scale rating 1/10) with all 3 patients having resolution of their pain within 4 days. There were no serious adverse events. Now that the safety of this dose level of MSCs has been shown, injection of the contralateral submandibular gland at the same dose level will be undertaken. We are opening a phase I clinical trial in 2023 in which patients undergo bilateral submandibular gland injection with interferon gamma stimulated MSCs. In order to provide the most benefit for patients, bilateral injection is recommended, as this will allow for the regeneration of both submandibular glands, which provide the majority of unstimulated saliva.

Additionally, the UW PACT has demonstrated stability of the cryopreserved MSC IMP after storage (see Appendix 19.4 for stability data). Each patient's MSC IMP was cryopreserved, thawed, culture-rescued, and formulated for injection in the already conducted pilot clinical study. The MSC IMP utilized for the second injection is composed of MSCs that were manufactured and cryopreserved at the same time as the MSCs for the first injection.

Each patient has cryopreserved autologous MSCs sufficient to allow for injection of the contralateral submandibular gland at dose level 0. We will utilize the cryopreserved MSCs for the contralateral gland injection, removing the need for another bone marrow aspiration and culturing of cells. The MSC IMP for the second injection will be identical to the first injection with the exception that these MSCs have been in cryopreservation longer.

6.0 THIS AMENDMENT WILL BE FORWARDED TO THE FDA FOR REVIEW PRIOR TO IMPLEMENTATION. STUDY OBJECTIVES AND ENDPOINTS

Objectives	Endpoints
Primary To evaluate the safety and tolerability of MSCs for subjects with xerostomia after radiation for HNC.	Recommended starting dose of MSCs for a Phase I dose-escalation study, determined by the proportion of subjects experiencing dose-limiting toxicity (DLT), where DLT is defined as: submandibular pain > 5 on a standard 10-point pain scale of 0-10 at 1-month after MSC injection OR any serious AE OR any of the selected toxicities listed in section 9.7 within one-month post-injection.
Secondary	

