7.0 STUDY DESIGN

7.1 General Design

This single-center, open-label, non-randomized, non-placebo controlled, single-group assignment, pilot study is designed to determine the safety and tolerability of autologous bone marrow-derived MSCs in patients with xerostomia after undergoing radiation therapy for HNC. A total of 6- subjects will be enrolled at UW-Madison for unilateral gland injection (dose level 0). Subject accrual will occur over 0.5 years with the total duration of the trial expected to be approximately 2.5 years.

Following the completion of screening/baseline procedures, and written consent, eligible subjects will undergo bone marrow aspirate in order to obtain MSCs. MSCs will be prepared as described in Section 9.2.

The MSC IMP (dose level 0) will be injected into one submandibular gland under local anesthesia, in the gland that received the lowest radiation dose. Patients with only one submandibular gland will be ineligible. All subjects will be called by a study coordinator 3 days (+/- 2 days) after injection to assess pain and will have a phone visit with a physician 1 week (+/- 2 days) after injection during which the investigator will assess pain and ask about the area of injection regarding redness and/or swelling. All subjects will complete a pain diary with daily entries over the first month to record the occurrence and severity of pain using a 0-10 visual analog scale and occurrence and severity of other adverse events (e.g., redness, swelling, warmth, tenderness, rash, pruritis, nausea, vomiting, fatigue). Patients will also keep a log of all pain medications taken including both narcotic and non-narcotic medications (e.g. ibuprofen, acetaminophen, etc.) for the first month. Subjects will complete 5 follow-up visits over the course of 24 months – at 1, 3, 6, 12, and 24 months following the intervention. Salivary collection for analysis as well as QoL surveys will be obtained at these visits.

Additional Gland Injection: The 6 subjects will be offered optional contralateral submandibular gland MSC injection at dose level 0 upon completion. The primary objective (1 month of follow-up after injection of MSCs) without any DLTs has now occurred.

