Subjects will also be offered injection of MSCs into the contralateral submandibular gland upon completion of the trial's primary objective (1 month of follow-up after injection of MSCs without any DLTs). The MSC IMP (dose level 0, from previously obtained bone marrow aspirate and culture) will be injected into the contralateral submandibular gland under local anesthesia. Secondary objectives will remain unchanged. Each subject will undergo salivary collection and completion of QoL forms just prior to second injection of MSC IMP. All subjects will complete follow up timepoints per the main study at 12 months (+/- 3 months) post second injection to analyze the benefit of the second injection by assessing secondary objectives including salivary amount and salivary QoL. This 12 month timepoint will allow for assessment of durable improvement, while not prolonging the overall study duration. Additionally, subjects will be monitored for AEs post-injection. All subjects will be called by a

study coordinator or physician 3 days (+/- 2 days) and 7 days (+/- 2 days) after injection to assess pain, redness, or other AEs. Subjects will also be seen 30 days (+/- 10 days), 90 days (+/- 14 days), 6 months (+/- 28 days), 12 months (+/- 3 months) and 24 months (+/- 3 months) after second MSC injection for safety evaluation and blood collection to assess for AEs.

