8.0 SUBJECT SELECTION

8.1 Inclusion & Exclusion Criteria

Eligibility will be determined by inclusion and exclusion criteria below and confirmed by medical record review as necessary.

Inclusion Criteria

1. Willing to provide informed consent.
2. Willing to comply with all study procedures and be available for the duration of the study.
3. Histological diagnosis of HNC and ≥ 2 years from completion of radiation treatment for HNC (\pm surgery, \pm chemotherapy), either clinically or radiologically NED, as assessed by ENT or Radiation Oncologist within 28 days of study registration
4. Individuals at least 18 years of age and no older than 90 years of age.
5. Xerostomia defined as $\leq 80\%$ of baseline (pre-radiation) salivary function per patient estimate
6. Karnofsky performance status ≥ 70 , patient eligible for bone marrow aspirate with wakeful anesthesia.
7. Radiographically confirmed bilateral submandibular glands
8. Females of childbearing potential must agree to have a negative urine or serum pregnancy test within 7 days prior to bone marrow biopsy. A female of child-bearing potential is any woman (regardless of sexual orientation, having undergone a tubal ligation, or remaining celibate by choice) who meets the following criteria:
 - Has not undergone a hysterectomy or bilateral oophorectomy; or
 - Has not been naturally postmenopausal for at least 12 consecutive months (i.e., has had menses at any time in the preceding 12 consecutive months).
9. Women of childbearing potential in sexual relationships with men must have used an acceptable method of contraception[§] for 30 days prior to study registration and agree to use an acceptable method of contraception[§] until 4 weeks after completing study treatment. Males must agree to avoid impregnation of women during and for four weeks after completing study treatment through use of an acceptable method of contraception.
[§]Note: Includes, but is not limited to, barrier with additional spermicidal foam or jelly, intrauterine device, hormonal contraception (started at least 30 days prior to study enrollment), intercourse with men who underwent vasectomy.
10. Laboratory values:
Hgb ≥ 9 g/dL (5.58 mmol/L)
Platelets $\geq 100,000/\mu\text{L}$
ANC $\geq 1000/\mu\text{L}$
PT/INR and PTT within normal limits based on age/sex
Serum creatinine within normal limits based on age/sex

Exclusion Criteria

1. History of sialolithiasis

2. Patients with one submandibular gland

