9.10 Study Procedural Intervention(s) Description

Pre-Intervention Bone Marrow Biopsy for MSC Collection

Each subject will undergo a bone marrow (BM) aspirate in order to obtain MSCs. Subjects will undergo BM aspiration for the collection of approximately 30 mL of BM aspirate in the UW Oncology Clinic by an experienced practitioner. Female subjects will have a urine pregnancy test which must be negative to participate. An IV will be placed for conscious sedation, if needed, and for blood collection following the aspiration procedure. If conscious sedation is chosen by the patient, IV sedative will be administered by a trained nurse who will monitor the subject throughout the procedure and recovery from sedation. For the BM collection procedure, the subject will be placed in a prone or side-lying position and the area over iliac crest will be anesthetized with a local anesthetic. The skin will be scrubbed with chlorhexadine and draped with sterile towels/drapes. Using sterile technique, the physician will insert a harvesting needle and aspirate BM into 2-4 10cc syringes, previously rinsed with 3000 units of heparin, collecting 5-10 ml at a time. After the first syringe is aspirated, the beveled needle may be turned 90 degree for three more turns and the aspiration repeated after each turn. Each syringe filled with bone marrow will be injected into a tube that has been prepared with Na Heparin. The collection tube will be labeled with a unique hMSC bank ID number. When all BM has been collected the harvesting needle will be removed and a dressing will be placed over the aspiration site. If subjects have received intravenous (IV) sedation, they will be observed for at least 1 hour or until fully recovered. In addition, subjects will receive a phone call from the research study coordinator within 3 +/- 2 days to review any potential side effects that might be attributable to the bone marrow aspiration.

MSC IMP Administration

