10.0 STUDY VISITS AND PROCEDURES

10.1 Study Calendar

The procedures performed at each study visit are listed in the table below.

Procedure/Visit	Screening	Baseline	Obtain MSCs ²	MSC IMP Injection	Follow-up visit						
					3-day phone call ⁹	1-week phone call ⁹	1-month	3-month	6-month	12-month	24-month
Visit window											
Day ± days	- 42 ± 14	- 42 ± 14	- 28 ± 14	0	3 ± 2	7 ± 2	30 ± 10	90 ± 14	180 ± 21	365 ± 21	730 ± 28
Informed Consent	X										
Review Eligibility Criteria	X										
Demographics	X										
Review Concomitant Medications	X				X	X	X	X	X	X	X
Dental Evaluation ⁵		X									
Obtain Medical History		X									
Physical Exam		X					X	X	X	X	X
Vital Signs ¹		X		X ³			X				
Bone Marrow Aspiration			X								
MSC IMP Injection				X							
AE Assessment Including Pain			X	X ⁴	X	X	X	X	X	X	X
Assessment of QoL, Salivary Collection		X					X	X	X	X	X
Ultrasound of Salivary Glands		X						X	X	X	
Collection of Pain Diary ⁶							X				
Blood (for banking)		X					X	X	X	X	X
Complete blood count, PT/INR and PTT, Creatinine		X					X ⁸	X ⁸			
Pregnancy test (urine or serum)			X ⁷	X ⁷							

¹ – Vitals include body weight, pulse rate, body temperature, blood pressure, and respiration rate. Height collected only at baseline.

² – Subjects will be contacted via phone 3 days +/- 2 days post bone marrow aspiration to assess for toxicities from aspiration by study coordinator

³ – Vitals to be obtained pre injection and 30 minutes +/- 10 minutes post injection. Weight only obtained pre injection.

⁴ – Subjects will be asked to verbally rate their pain 30 minutes post MSC administration.

⁵ – Dental examination with x-rays within 6 months of enrollment by patient report

⁶ – Patients without chronic pain will be instructed to refrain from narcotic pain medication for 3 days prior to their scheduled pain assessment. Patients with chronic pain will be instructed not to increase their baseline narcotic pain medication for 3 days prior to scheduled pain assessment.

⁷—Within 7 days prior to MSC collection and confirmation of appropriate contraception prior to injection.

⁸—CBC only during follow up

⁹-Subjects will be contacted via phone 3 days (+/- 2 days) and 7 days +/- 2 days post MSC IMP Injection to assess for toxicities from injection by study coordinator or physician.

Sub study calendar

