Informed Consent	Screen/Injection of MSC's	Phone call (3 days +/- 2 days) ¹	Phone call (7 days +/- 2 days) ¹	30 day visit (+/-10 days)	90 days (+/- 14 days)	6 months (+/- 28 days)	12 months (+/- 3 months)	24 months (+/- 3 months)
Review Eligibility Criteria	X							
Review Concomitant Medications	X							
Vital Signs ²	X							
Physical	X			X	X	X	X	X
MSC IMP Injection (contralateral neck)	X							
AE Assessment Including Pain	X ³	X	X	X	X	X	X	X
Assessment of QoL, Salivary Collection	X			X	X	X	X	
Collection of Pain Diary				X				
Complete blood count	X			X ⁴	X ⁴			

¹Subjects will be contacted via phone 3 and 7 days +/- 2 days post MSC IMP Injection to assess for toxicities from injection by study coordinator or physician

²Vitals to be obtained pre injection and 30 minutes +/- 10 minutes post injection. Weight only obtained pre injection.

³— Subjects will be asked to verbally rate their pain 30 minutes post MSC administration. Patients without chronic pain will be instructed to refrain from narcotic pain medication for 3 days prior to their scheduled pain assessment. Patients with chronic pain will be instructed not to increase their baseline narcotic pain medication for 3 days prior to scheduled pain assessment

⁴CBC only during follow up

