- QoL assessment
- Adverse event assessment
- Collection of blood sample for banking purposes

Twelve Month Follow-up Visit (365 days \pm 21 days)

- Review current medications being taken
- Physical exam including weight
- Salivary collection
- US of salivary glands
- QoL assessment
- Adverse event assessment
- Collection of blood sample for banking purposes

Twenty Four Month Follow-up Visit (730 days \pm 56 days)

- Review current medications being taken
- Physical exam including weight
- Salivary collection
- QoL assessment
- Adverse event assessment
- Collection of blood sample for banking purposes

Screening/MSC IMP Administration in Contralateral Gland

- Physical exam including weight
- Salivary Collection
- QoL assessment
- MSC injection (see section 9.6)
- Vital signs

Three Day Telephone Call (3 days \pm 2 days)

- Adverse event assessment

Seven Day Telephone Call After Contralateral Injection (7 days \pm 2 days)

- Adverse event assessment

Thirty Day Follow-up Visit After Contralateral Injection (30 days \pm 10 days)

- Physical exam including weight
- Adverse event assessment
- Complete Blood Count
- Salivary Collection
- QoL assessment

Ninety Day Follow-up Visit After Contralateral Injection (90 days \pm 14 days)

- Physical exam including weight
- Adverse event assessment
- Complete Blood Count
- Salivary Collection
- QoL assessment

Six Month Follow-up Visit (180 days +/- 28 days)

- Physical exam including weight
- Salivary collection
- QoL assessment
- Adverse event assessment

Twelve Month Follow-up Visit After Contralateral Injection (12 months \pm 3 months)

- Physical exam including weight
- Adverse event assessment
- Salivary collection
- QoL assessment

Twenty Four Month Follow-up Visit (730 days +/- 3 months)

- Physical exam including weight
- Adverse event assessment

Note: This twenty four month visit will be the subject's final study visit.

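### No pregnancy test or contraception check is scheduled before the second injection, because testing is tied to a marrow aspiration that is not repeated

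*Combined protocol and SAP*

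**What the plan says.** Three places set the timing of the pregnancy test, and all three refer to marrow collection.

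- Section 8.1, inclusion criterion 8: women of childbearing potential "must agree to have a negative urine or serum pregnancy test within 7 days prior to bone marrow biopsy".
- Section 9.10, under the marrow procedure: "Female subjects will have a urine pregnancy test which must be negative to participate".
- Section 10.1, main calendar, footnote 7: "Within 7 days prior to MSC collection and confirmation of appropriate contraception prior to injection". The pregnancy row carries this footnote at both the collection column and the first-injection column.

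The sub-study adds a second dose. Section 7.1 says: "The 6 subjects will be offered optional contralateral submandibular gland MSC injection at dose level 0 upon completion". The cells for it come "from previously obtained bone marrow aspirate and culture", and section 5.5 describes the use of stored cells as "removing the need for another bone marrow aspiration and culturing of cells".

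The sub-study calendar in section 10.1 marks an eligibility review at the combined screening and injection visit. As far as it can be read, it has no pregnancy-test row, and none of its four footnotes mentions pregnancy or contraception. Exclusion 11 bars pregnant women, section 8.7 allows withdrawal for pregnancy, and section 15.11 requires pregnancies to be reported. Inclusion criterion 9 requires contraception until 4 weeks after study treatment is complete. Section 9.9 still describes a protocol with one administration.

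**The concern.** The event that triggers the test happens once, but dosing can happen twice. At the second dosing visit the investigator reviews eligibility, including exclusion 11, without a new test result. A subject who knows that she is pregnant would be caught. One with an early, unrecognised pregnancy would not, and withdrawal and reporting also depend on the pregnancy being known. Criterion 8 shows that the plan does not rely on self-report, since it asks for a test even from women who are celibate or have had a tubal ligation. At stake is a second exposure to a product that section 5.4 calls first-in-human, in a subject whom the protocol itself excludes. No endpoint, sample size or analysis is affected.

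**Working it through.** The plan gives no figure to reproduce. The check is a comparison of the two calendars, followed by date arithmetic.

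**1. Is the omission real, or lost in text extraction?** The header of the sub-study calendar is damaged, so a lost row cannot be fully excluded. The footnotes can be compared:

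| Main-calendar footnote | Subject | In the sub-study calendar? |
|---|---|---|
| 1 | Definition of vital signs | No |
| 2 | Call after aspiration | Does not apply |
| 3 | Vital signs around injection | Yes |
| 4 | Pain rating at 30 minutes | Yes |
| 5 | Dental examination | Does not apply |
| 6 | Narcotic restriction | Yes |
| 7 | Pregnancy test and contraception | **No** |
| 8 | Blood count only at follow-up | Yes |
| 9 | Phone calls after injection | Yes |

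Apart from the definition in footnote 1, footnote 7 is the only one relevant to an injection visit that was not carried over. The visit list in section 10.3 headed "Screening/MSC IMP Administration in Contralateral Gland" also has no test, but this carries no weight: section 10.3 omits the main-study test too.

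**2. How old would the last scheduled test be at the second injection?**

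Inputs:
- Marrow collection on day -28 ± 14, so between day -42 and day -14 (section 10.1).
- Test within 7 days before collection (criterion 8).
- One-month visit on day 30 ± 10, so day 20 at the earliest (section 10.1).
- Second injection offered once the one-month primary objective is complete (section 7.1).

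The main calendar can be read in two ways:
- *The mark at the first injection means a test on day 0.* Minimum age = 20 - 0 = **20 days**.
- *That mark means contraception confirmation only, so the last test is at collection.* The latest collection is day -14, with the test on the same day at best. Minimum age = 20 + 14 = **34 days**.

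Both exceed the 7-day limit that the plan sets before collection.

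**3. Why it is probably much older.** Sections 5.5 and 7.1 treat the primary objective as met for the trial as a whole. Section 9.7 requires at least 14 days between one subject's injection and the next. With 6 subjects that is 5 × 14 = 70 days from the first subject to the last. For the subject treated first, the minimum becomes 70 + 20 = 90 days on the first reading and 90 + 14 = 104 days on the second. These are theoretical lower bounds. The documents give no actual dates and no maximum interval.

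**The case against.** **It may affect nobody.** The second injection is offered to a closed group of 6 whose sex and childbearing status the team already knew when the amendment was written. This stands. The documents do not give the number of women of childbearing potential, and it may be zero.

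**The eligibility review is a safeguard.** It brings criterion 9 and exclusion 11 back into view and could prompt a question about contraception. A reader might infer that exclusion 11 has no force at the second injection. The documents do not support that: a known pregnancy would be caught. What remains is the unrecognised pregnancy.

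**The evidence is an absence in a damaged table.** This is a fair limit on certainty. The footnote comparison makes accidental loss unlikely but does not rule it out.

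**A 7-day rule at injection may be stricter than the plan ever was.** If the first injection needed only a contraception check, its test could be 14 days old (14 + 0) to 49 days old (42 + 7), and 34 days lies inside that range. So it cannot be said that the second injection breaks an existing 7-day rule for injections; that rule governs collection. The objection does not defend the gap, because nothing limits the age of the result at the second injection.

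**Contraception still applies.** A reader might infer from criterion 9, together with section 9.9, that the contraception duty lapses before the second injection. The more natural reading is that treatment is complete only after the last injection received. The wording is loose enough to deserve a clarification, but it does not show a lapse.

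**Conclusion.** The point holds in limited form. Every stated test timing is tied to marrow collection, the second injection involves no collection, and the readable sub-study calendar schedules neither a pregnancy test nor a contraception check. Followed as written, the plan could re-dose a woman with an unrecognised pregnancy whom exclusion 11 bars. The result relied on would be at least 20 or at least 34 days old, depending on how the main calendar is read, and probably older.

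This rests on three assumptions: no row was lost from the sub-study calendar, the second injection does not precede the earliest one-month visit, and at least one of the 6 subjects is of childbearing potential. The last cannot be checked from the documents. Nothing in them shows that a pregnant woman was or will be dosed. The change is worth making because it is a cheap gain in participant safety.

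**What to change.** For women of childbearing potential in the sub-study:

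1. Require a negative urine or serum pregnancy test within 7 days before, or on the day of, the second injection.
2. Confirm contraception at that visit.
3. Add both to the sub-study calendar in section 10.1 and to the contralateral-injection visit in section 10.3.
4. State in criterion 9 that the 4 weeks run from the last injection received.

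If none of the 6 subjects is of childbearing potential, record that in the sub-study text instead of testing.

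The cost is one routine test at an existing visit for at most 6 subjects, possibly none, plus a few lines of text. The downside is that a positive or unclear result would delay or cancel a prepared dose. Under section 9.2 the cells are thawed and cultured for 16 hours before injection, so testing before the thaw would reduce that loss.
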